9.2 Sample Size and Randomization

Based on our past trials, we project 95% retention at 4-weeks. We estimated standard deviations of each outcome based on patients in a similar project with analogous eligibility criteria, and conservatively estimated pre-post correlations to be 4%-7% smaller than the values in this study. Assuming a sample size of 316, of which 280 meet all eligibility criteria and 92% of enrolled participants are retained to 4 weeks, the table below displays minimum detectable effect sizes for a) main effects of each protocol component, b) pairwise interactions between components, c) comparison of mean outcome between two levels of one component at a fixed level of another component, d) main effects of the 3 components in subgroup analyses involving half the participants, and e) pairwise interactions between 2 components in subgroup analyses with half the participants. This sample size provides at least 80% power to detect the MCID or hypothesized effect sizes for the main effects of each component for all outcomes, and for analyses of main effects in subgroups and conditional comparisons for each outcome except global stiffness. Power is more limited for secondary aims, such as pairwise interactions within subgroups.

	Assumptions for Outcome Measures in Project			
	Global Stiffness (N)	Multifidus Activation (mm)	Oswestry	Numeric Pain Rating
Assumption				
Mean (SD)	5.55 (1.60)	2.60 (0.124)	24.3 (14.9)	5.06 (2.12)
Pre-post score correlation	0.80	0.70	0.70	0.45
MCID or hypothesized effect size from past work	0.40	0.074	6.0	2.0
Type of effect	Detectable Effect Size			
Main effect	0.37	0.034	4.12	0.76
Pairwise interaction	0.74	0.064	8.24	1.53
Conditional comparison	0.53	0.045	5.83	1.08
Main effect in 50% of subjects	0.53	0.045	5.83	1.08
Interaction in 50% of subjects	1.05	0.091	11.65	2.16

Table. Assumptions and detectable effect sizes informing sample size for the project.

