Adjusted means with CIs will be provided for each treatment combination. Interaction plots will be used to depict significant interactions and linear contrasts constructed to evaluate the effect of each intervention conditional on the presence or absence of the other intervention. To account for 2 primary outcomes, each of the hypothesis tests noted above will be performed with 2-sided $\alpha=0.025$ and confidence intervals will be constructed using a confidence coefficient of 0.975. The indicated comparisons at 4-weeks will be given primary emphasis in evaluating the effects of each intervention. Comparisons at 3-months will evaluate persistence of effects following intervention.

Primary Aim #2: The OSW and NPRS will be co-primary outcomes for evaluating the effects of the 3 SMT protocol components on patient centered outcomes. The same analytic approach described above will be used. To account for 2 outcomes, we will again apply a 2-sided $\alpha=0.05$ and 97.5% CIs for statistical inference.

Secondary Aim #1: It is unknown how early SMT response may affect response to additional intervention. We will examine this question by evaluating responder status after 1 week as a possible effect moderator by adding a main effect for responder status and interaction terms between responder status and the indicator variables for treatments (and treatment combinations) which are retrained in the final simplified models for the different outcomes developed using the BIC criteria for each of the co-primary outcomes for the primary aims 1 and 2. Statistically significant interactions between responder status and main effect and/or interaction terms between treatment intervention components will be interpreted as suggesting effect moderation. Recognizing that tests for interactions have limited statistical power, we will also fit the simplified models developed in Aims 1 and 2 separately under the presence and absence of each factor (dichotomizing using a median split for continuous factors), and graphically display the estimated treatment effects at both levels of responder status. Recognizing the potential for lower statistical power, the results of Secondary Aim #1 will be interpreted as exploratory.

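### Primary Aim 2 tests its two co-primary outcomes at α = 0.05 but reports 97.5% CIs, so the tests lack the two-outcome adjustment and can contradict the intervals

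*Combined protocol and SAP*

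**What the plan says.** Section 9.6 (Data Analyses) names the Aim 2 outcomes: "The OSW and NPRS will be co-primary outcomes for evaluating the effects of the 3 SMT protocol components on patient centered outcomes". It carries the method over from Aim 1: "The same analytic approach described above will be used". It then sets the inferential level: "To account for 2 outcomes, we will again apply a 2-sided $\alpha=0.05$ and 97.5% CIs for statistical inference".

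The Aim 1 rule to which this refers back is in the preceding paragraph of the same section. For the intervals: "confidence intervals will be constructed using a confidence coefficient of 0.975". For the tests: "each of the hypothesis tests noted above will be performed with 2-sided $\alpha=0.025".

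No other section gives a test level for Aim 2. There is no hierarchical order between the two outcomes and no requirement that both succeed; either could have justified 0.05 per outcome. The Secondary Aim 2 paragraph of section 9.6 again works with 97.5% (simultaneous) intervals for each outcome.

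**The concern.** The Aim 2 sentence conflicts with the plan in two ways. It says it repeats the Aim 1 allowance for two outcomes but gives the unadjusted level. It also pairs a two-sided 0.05 test with a 97.5% interval, although a 97.5% interval corresponds to a test at 1 − 0.975 = 0.025.

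This is the decision threshold for the patient-centred primary outcomes, which section 9.6 says will be preferred when optimized protocols are interpreted. An analyst who follows the text literally can declare a component effective while the interval beside it includes zero. The plan does not say which governs, so the choice could be made after the results are known.

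**Working it through.** **1. Inputs**

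- Section 9.2: 280 enrolled, 92% retained to 4 weeks, so N = 280 × 0.92 = 257.6.
- Section 9.2: power 80%. SDs are 1.60 (global stiffness), 0.124 (multifidus), 14.9 (Oswestry) and 2.12 (pain). Pre-post correlations are 0.80, 0.70, 0.70 and 0.45, in the same order.
- Précis: equal allocation to 8 combinations, so each main effect compares two halves of the sample.
- The table in section 9.2 states no alpha.

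**2. Reproducing the plan's detectable main effects**

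With baseline adjustment as in ANCOVA:

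SE = SD × √(1 − ρ²) × 2/√N, and detectable effect = (z(1−α/2) + 0.8416) × SE.

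The multiplier is 2.2414 + 0.8416 = 3.083 at α = 0.025 and 1.9600 + 0.8416 = 2.802 at α = 0.05.

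Oswestry: SE = 14.9 × √0.51 × 2/√257.6 = 1.326.

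| Outcome | Table | α = 0.025 | α = 0.05 |
|---|---|---|---|
| Global stiffness | 0.37 | 0.369 | 0.335 |
| Multifidus | 0.034 | 0.0340 | 0.0309 |
| Oswestry | 4.12 | 4.09 | 3.71 |
| Numeric pain rating | 0.76 | 0.73 | 0.66 |

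The first two rows calibrate the method: they are Aim 1 outcomes, for which 0.025 is the stated level, and they reproduce at that level. Oswestry, an Aim 2 outcome, also reproduces at 0.025. A t-based version gives 4.11 at 0.025 and 3.73 at 0.05. Pain rating matches at neither level, though 0.025 is closer (4.3% below the table, against 13.0% below).

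The Oswestry result does not depend on the retention assumed. With N = 266 (the 95% retention also mentioned in section 9.2), the detectable effect is 4.02 at 0.025 and 3.66 at 0.05. With all 280 it is 3.92 and 3.56.

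**3. Where test and interval disagree**

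They disagree when |z| lies between 1.960 and 2.241.

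- Oswestry: 1.960 × 1.326 = 2.60 to 2.241 × 1.326 = 2.97 points.
- Pain: SE = 2.12 × √(1 − 0.45²) × 2/√257.6 = 0.236, giving 0.46 to 0.53 points.

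**4. False-claim rate for one effect across the two outcomes**

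Upper bound: 2 × 0.05 = 10% as written, 2 × 0.025 = 5% if adjusted. With independent outcomes: 1 − 0.95² = 9.75% against 1 − 0.975² = 4.94%. The plan gives no correlation between Oswestry and pain, so a range is assumed (bivariate normal):

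| Assumed correlation | 0.05 each | 0.025 each |
|---|---|---|
| 0 | 9.75% | 4.94% |
| 0.3 | 9.51% | 4.84% |
| 0.5 | 9.07% | 4.65% |
| 0.7 | 8.35% | 4.30% |

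The rate roughly doubles throughout this range.

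**5. Power if Aim 2 is tested at 0.025**

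- Oswestry at its MCID of 6: 6/1.326 − 2.241 = 2.28, a power of 98.9%.
- Pain at its MCID of 2: 2/0.236 − 2.241 = 6.2, a power above 99.9%.

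**The case against.** The strongest reply is that the intention is clear and only one number is wrong. The sentence keeps 97.5% intervals, says it is accounting for two outcomes, and follows a statement that the Aim 1 approach applies. Unlike the Aim 1 sentence, it does not say that the level applies to each test, so 0.05 might be meant as the overall level. The practical reach is also limited. The adjusted intervals would expose any conflict, the disputed estimates are at most about half the Oswestry MCID of 6 and about a quarter of the pain MCID of 2, and the choice of optimized combinations uses BIC and simultaneous 97.5% intervals rather than this test level.

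Much of this stands. The adjustment is missing from the tests, not from the intervals, and a slip is the likeliest explanation. The use of 0.025 in the sample-size table is an inference, supported by only one of the two Aim 2 outcomes. Multiplicity across the three components is a separate question that neither aim addresses and this correction would not resolve.

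None of it removes the conflict. The wording refers back to a paragraph in which the stated alpha is per test, so the literal reading is 0.05 per test. If an overall 0.05 was meant, the per-test level is still 0.025 and still needs to be stated.

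**Conclusion.** The concern holds. The Aim 2 test level conflicts with the interval level in the same sentence and with the Aim 1 rule it claims to repeat, and nothing elsewhere in the plan justifies 0.05 per outcome. Read literally, it roughly doubles the false-claim rate for one effect across the two outcomes: 9.75% against 4.94% if independent, and 8.35% against 4.30% at an assumed correlation of 0.7. It also leaves a band of p-values from 0.025 to 0.05 in which test and interval give opposite answers. The size of that band in outcome units rests on the SDs, correlations and retention in section 9.2; the contradiction itself rests on no assumption. Because this is the decision threshold for a primary aim, it should be settled before any outcome data are analysed.

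**What to change.** In the Primary Aim #2 paragraph of section 9.6, replace 0.05 with 0.025 and state that it is the two-sided level for each test on each of the Oswestry and the numeric pain rating, with matching 97.5% intervals. If an overall 0.05 was intended, say so and give 0.025 as the per-test level. It would also help to state the alpha behind the section 9.2 table and to recheck its pain-rating entry of 0.76.

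The cost is one number in the text. The sample size does not change: the Oswestry detectable effect in the table already agrees with 0.025, and power at both MCIDs stays above 98%.

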6.2.2.3 Randomization

Following baseline assessment all participants will receive 2 SMT treatment sessions in the next week. Randomization to additional treatment will be done at the 1-week assessment. A randomization schedule will be developed prior to enrollment by co-investigator [name], Director of the Study Design and Biostatistics Center (SDBC) in the CCTS at the University of Utah. Blocked randomization with block sizes of 4 or 6 will be used. Randomization will be stratified based on site (Utah or Alberta) and responder status after 2 SMT sessions (based on re-assessment of the OSW) to balance these variables. At the 1-week assessment the study coordinator or research assistant will look up the participant in the study database and open the Responder & Randomization Status

form in REDCap. This form will display the Oswestry score from the baseline assessment and the calculation of score change. The percent change between baseline and 1-week scores determines responder status (>50% improvement = “responder”; <50% improvement= “non-responder”). Once the responder status is entered the study staff will select the randomize button on the screen to trigger study assignment based on the allocation table provided by the biostatistician, provided all of eligibility criteria are met and the participant has been assigned to one of the two study sites. If any of these criteria are not valid a warning message will be displayed indicating the criteria issue(s) and the randomization will not be completed.

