9.6 Data Analyses

Primary Aim 1: Spine stiffness and multifidus activation will be co-primary outcomes for evaluating effects of SMT protocol components on SMT mechanisms. The effect of intervention components (A additional SMT; B multifidus activation; C mobilizing exercises) on each outcome will be evaluated using linear mixed models to relate mean levels of each outcome at 1-, 4-weeks and 3-months to indicator variables to represent the main effects of each interventions (A, B, C) as well as each pairwise interaction between the interventions (AxB, AxC, BxC) and the 3-way interaction (AxBxC). 1-week assessment, which occurs just before randomization, will serve as the baseline for these analyses and the model will be assumed equal between the randomized groups. This model, sometimes referred to as a constrained longitudinal model, leads to adjustment for baseline levels as in analysis of covariance (ANCOVA), which has been shown to remove conditional bias in treatment group comparisons due to chance imbalances and improve statistical power over unadjusted comparisons. An unstructured covariance matrix will be used to account for correlation of serially measured outcome scores in the same subject. By using an unstructured covariance matrix, the model will constitute a special case of a general linear mixed model which avoids imposing specific assumptions concerning distribution of random effects. This modelling approach is recommended in randomized trials when the number of follow-up outcome assessments is small. Restricted maximum likelihood estimation will be used for estimation of parameters and their associated standard errors.

Linear mixed effects analysis will provide estimates and CIs for the following quantities for each outcome at both 4-week and 3-month assessments: a) Main effects evaluating effects of each of the 3 interventions while averaging over the levels of the other 2 interventions. b) Three pairwise interactions evaluating if the effect of an intervention differs between levels of another interventions, while averaging over levels of the 3rd intervention. Pairwise interactions will inform whether the effects of each intervention pair are additive, synergistic or antagonistic. c) 3-way interaction evaluating if each pairwise interaction differs depending on the 3rd intervention.

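### Secondary Aim 1 names no responder-by-visit term; fitted literally, its model would show spurious moderation on the Oswestry

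*Combined protocol and SAP*

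**What the plan says.** Four statements in the combined protocol and SAP meet here.

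- Section 9.6, Primary Aim 1, uses "linear mixed models to relate mean levels of each outcome at 1-, 4-weeks and 3-months to indicator variables" for the components and their products. It adds that the "1-week assessment, which occurs just before randomization, will serve as the baseline for these analyses", with the randomized groups taken as equal at that visit. The 1-week score is therefore a modelled response, and component effects begin after it.
- Section 6.2.2.3 defines the moderator: "The percent change between baseline and 1-week scores determines responder status", with a cut at 50% improvement on the Oswestry.
- Section 9.6, Secondary Aim #1, tests moderation "by adding a main effect for responder status and interaction terms between responder status and the indicator variables for treatments". The component terms carried forward are those in the "final simplified models for the different outcomes developed using the BIC criteria".
- The same paragraph says that significant responder interactions "will be interpreted as suggesting effect moderation". It also plans separate fits by responder status, displayed graphically, and labels the aim exploratory.

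No responder-by-visit term is mentioned. The text does not say that the responder effect is constant over visits, nor that it varies.

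**The concern.** Responders are selected partly for a low 1-week Oswestry, so the gap between them and non-responders is at its widest at week 1. With a pre-post correlation of 0.70 (section 9.2), part of that gap should close by week 4 without any treatment effect.

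A model with a single responder effect must hold the gap equal at all three visits. If the components are coded 0/1 and act only after week 1, the one place where the model can let the gap narrow is the set of responder-by-component terms. These come out positive on a scale where higher is worse, so the added components look less helpful in responders.

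The stake is the stated secondary hypothesis that early response moderates outcome, which such an artefact would appear to confirm. It could also colour how the responder-specific optimization that Secondary Aim #2 says will be considered is read, although that is a separate model and need not share the problem.

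**Working it through.** **Inputs from the documents.** 280 enrolled and 92% retained, so N = 280 × 0.92 = 257.6; Oswestry SD 14.9; pre-post correlation 0.70; MCID 6 points; entry score at least 20; responder cut 50%; expected responder rate 35% to 45%; randomization stratified by responder status.

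**Assumed, because the documents do not give them.** Day-0 Oswestry normal with mean 36 and SD 12, truncated at 20; correlation 0.55 between day 0 and 1 week; 4-week score dependent on responder status only through the 1-week score, with slope 0.70.

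**1. The plan's own figure.** The documents give no figure for this bias, but the detectable main effect checks the inputs:

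(z₀.₉₈₇₅ + z₀.₈₀) × 2 × SD × √(1 − ρ²) / √N = (2.241 + 0.842) × 2 × 14.9 × √0.51 / √257.6 = 4.09

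The plan states 4.12. At two-sided 0.05 the result is 3.71, so the table matches 0.025.

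**2. The gap.** The assumed inputs give 34% responders and a responder gap of −22.8 points at 1 week. At 4 weeks it is −22.8 × 0.70 = −16.0, a narrowing of 6.8 points.

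**3. Where the 6.8 points go.** As an approximation, let the common responder effect stay at the 1-week gap. The responder-by-component terms must then reproduce a constant 6.8 at week 4. Let S be the number of kept components that a participant receives. The least-squares coefficient per component is 6.8 × E[S]/E[S²].

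- One kept: E[S] = 0.5, E[S²] = 0.5, giving 6.8.
- Two kept: E[S] = 1, E[S²] = 1.5, giving 4.5.
- Three kept: E[S] = 1.5, E[S²] = 3, giving 3.4.
- All seven terms: every treated cell takes 6.8 and the untreated cell 0. The averaged main-effect interaction is 6.8/4 = 1.7.
- −1/+1 coding: E[S] = 0, giving 0.

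**4. Simulation.** Three visits, unstructured covariance, iterated GLS, N = 258, 500 to 1,000 runs, component effects zero, no moderation, kept terms fixed in advance, constant responder effect with 0/1 indicators:

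| Terms kept | Approximation | Simulated false 4-week interaction | Rejection per component at 0.05 |
|---|---|---|---|
| One component | 6.8 | +6.3 | 85% (80% at 0.025) |
| Two components | 4.5 | +4.2 to +4.4 | 44% to 48% |
| Three components | 3.4 | +3.2 to +3.5 | 25% to 29% |
| All seven terms | 1.7 | +1.7 | about 10% |

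Responder rates of 40% and 46% give +6.2 to +6.3 (89%) with one component and +3.2 to +3.3 (26% to 28%) with three. Equal true effects of −4 per component in both strata leave the three-component bias at +3.1 to +3.4. A separate simulation of the three-component model under other assumed correlations gave +2.8 to +4.0 points and 21% to 41% per component.

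**5. Dependence on the gap (three components).** Gap unchanged: bias 0, rejection 4% to 5%. Gap falls 15%: about +1.5 points, 8% to 11%. Gap falls 50%: about +5.2 points, 52% to 57%.

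**6. Alternatives.** With a responder effect per visit, the false interaction is within about 0.2 points of zero and rejection is 4.3% to 7.0%. With the constant effect and effect coding, bias is within 0.45 points and rejection 3.4% to 6.4%. Separate fits by responder status differ by −0.14 points on average, with 6.8% rejection.

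**7. The BIC step.** The hierarchical search of Secondary Aim #2 (19 models) was run 3,000 times with no component effect. At least one term was kept in 4.7% of runs on the 4-week outcome and in 1.3% on both follow-ups jointly. All three components were never kept.

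**The case against.** The strongest reply is that a visit-constant effect is a reading, not a statement. Section 9.6 uses main effect loosely. For the components it promises estimates "for each outcome at both 4-week and 3-month assessments: a) Main effects evaluating effects of each of the 3 interventions", so the term there means one effect per visit, and the responder effect may be meant the same way. This stands, and it makes the point conditional. However, that visit-specific list covers only the interventions and their interactions, and responder status is not in it. The terms listed for Secondary Aim #1, taken literally, are one added effect plus products with indicators.

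The bias also needs 0/1 coding. Effect coding would suit the plan's averaged main effects and its description of a factorial analysis of variance, and it removes the bias. The text does say indicator variables, which ordinarily means 0/1.

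A reader might infer several stronger things that the documents do not support:

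- *That false moderation would be common even if no component works.* Simulating the three-component model under a complete null gives at least one false finding in 60% to 88% of runs. That skips the BIC step, which would rarely leave a term to test. The bias matters when a component works and is kept.
- *That using the 1-week score both as baseline response and to define responders is itself the error.* Randomization follows that visit and is stratified by responder status, so the double use does no harm once the gap may differ by visit.
- *That every outcome is affected.* Responder status comes from the Oswestry alone. Pain, stiffness and multifidus activation would be affected only if their responder gap changes after week 1, and they were not simulated.
- *That the primary aims are compromised.* Their models contain no responder term.

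The exploratory label and the separate fits soften the consequence. But the reason given for the label is low power, which warns of missed moderation rather than false moderation. The formal criterion is the interaction test, not the display.

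**Conclusion.** The point holds in conditional form. If the listed terms are fitted literally, the Oswestry moderation test in Secondary Aim 1 is biased towards showing components as less helpful in responders. For components kept by BIC, the false 4-week interaction runs from about +3 points with three kept to about +6 with one kept; the latter equals the 6-point MCID. It is smaller, about +1.7, if all seven terms are kept.

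These sizes rest on the assumed day-0 distribution and correlations, and on a gap that narrows by about 30% (6.8/22.8). Section 3 says the persistence of early improvement is unknown, so the size cannot be fixed in advance. The direction follows from any narrowing. Because the listed model gives a wrong answer when followed to the letter, this is more than a missing detail, although the team may already intend the sound version.

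**What to change.** In section 9.6, Secondary Aim #1, state that responder status enters with a separate effect at 1 week, 4 weeks and 3 months, and that responder-by-component terms are tested at 4 weeks and at 3 months. Three responder effects replace one, so the cost is two parameters per outcome. Data collection and sample size do not change. State the coding of the components as well; −1/+1 fits the plan's averaged main effects.

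An acceptable alternative is an ANCOVA at each follow-up on the 1-week score, responder status, the kept components and their responder interactions. The same sentence should apply to all four outcomes, which settles the question for those not examined here.

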1.2 Secondary Objectives

- I. Explore the moderating effect of responder status after 2 SMT sessions. We hypothesize that responder status after 2 sessions will moderate mechanistic and patient-centered outcomes.
- II. Define optimized SMT protocol(s) based on combined results of the primary and secondary aims. Optimized protocols will be considered as the combination of components that maximize improvement in patient-centered outcomes at 3 months while also improving SMT mechanisms to the greatest extent.

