3. STUDY DESIGN

We will use a factorial design examining 3 intervention components (additional SMT, mobilizing and multifidus activating exercise) provided in 8 different combinations following provision of 2 SMT treatment sessions as in our prior work. We will recruit 316 subjects with non-specific LBP with the goal of enrolling 280 subjects after all eligibility screening are complete. All subjects will receive the 2-session SMT protocol used in our prior studies. At the third session subjects will be categorized as SMT responders or non-responders based on our previously-validated threshold of 50% improvement on the Oswestry (ODQ). Randomization to subsequent treatment will be stratified based on responder status. This will allow us to examine the moderating effects of early clinical response. In our prior studies 35%-45% of individuals with LBP are responders to SMT after 2 sessions. What is unknown is the persistence of the improvement observed in early responders and whether or not persistence can be augmented through additional SMT and/or co-interventions working on the same causal pathways as SMT. Likewise, it is unknown from our prior work if early non-responders can be converted to responders with additional SMT and/or co-interventions. Therefore, we will randomly assign subjects to receive 6 additional sessions (or no additional treatment) provided over 3 weeks with varied combinations of additional SMT and exercise co-interventions. We chose 6 additional sessions based on work related to SMT dose-response reporting only modest difference in clinical outcomes in subjects receiving 9-12 sessions relative to 3-6 SMT sessions without co-interventions. Outcomes including assessments of

Outline of research design (LM = lumbar multifidus)

mechanisms and patient-centered outcomes will be examined at baseline and after 1 week (end of phase I), 4 weeks (primary outcome - end of phase II), and after 3 months (long-term outcome).

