Secondary Aim #2: In order to assess which intervention component combinations provide optimal outcomes, we will first simplify the fully saturated factorial analysis of variance model by comparing the Bayes Information Criterion (BIC) among all possible models including different combinations of main effects, pairwise interactions and the 3-way interaction which satisfy the hierarchical consistency constraint that the main effects corresponding to each term in a pairwise interaction are retained in models with pairwise interactions, and all component main effects and pairwise interactions are retained when considering the 3-way interaction. This will result in a more parsimonious model to increase statistical power. Then, using the simplified model, for each outcome we will use a simulation approach to derive simultaneous 97.5% CIs for all comparisons of estimated mean outcome under each possible treatment combinations (No further treatment, A, B, C, AxB, AxC, BxC, AxBxC). After ordering the treatment combinations in accordance with the observed mean outcome, the simultaneous CIs will be used to identify which combinations are statistically indistinguishable from the optimum treatment, thus identifying a set of candidate options for the best combination of treatments. This process will be applied for both mechanistic and patient-centered outcomes. We anticipate that more than one combination will be considered optimal for different outcomes, and that the combinations that are optimal will differ for different outcome measures. Our interpretation of optimized protocols will give preference to longer term outcomes (ie, 3-month scores) and patient-centered outcomes. We will also consider an application of the robust modelling approach to derive a model for the optimum combination of components as a multivariate function which jointly incorporates each the potential effect modification of week 1 responder status in the same model. This approach will estimate the combination of components providing the optimum expected outcome for each participant based on their responder status after 1 week.

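### Responder moderation is committed only for components that survive a BIC selection without responder status, so an effect largely confined to one stratum can go untested and unreported by stratum

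*Combined protocol and SAP*

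**What the plan says.** Secondary Objective I (section 1.2) is the moderating role of early response: "We hypothesize that responder status after 2 sessions will moderate mechanistic and patient-centered outcomes". Section 3 gives the clinical motive. It asks whether responders' gains can be made to last or be increased, and notes that "it is unknown from our prior work if early non-responders can be converted to responders with additional SMT and/or co-interventions".

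The analysis is in section 9.6 and has three parts.

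- **Selection.** Under Secondary Aim #2 the saturated factorial model is simplified by "comparing the Bayes Information Criterion (BIC) among all possible models including different combinations of main effects, pairwise interactions and the 3-way interaction", subject to a hierarchy rule. Responder status is not among the candidate terms.
- **Moderation test.** Under Secondary Aim #1 a responder main effect is added, together with "interaction terms between responder status and the indicator variables for treatments (and treatment combinations) which are retrained in the final simplified models".
- **Back-up for low power.** In the plan's words, "we will also fit the simplified models developed in Aims 1 and 2 separately under the presence and absence of each factor". Treatment effects are then plotted at both levels of responder status.

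One further route appears under Secondary Aim #2: "We will also consider an application of the robust modelling approach to derive a model for the optimum combination of components", which would include effect modification by responder status. It is optional and carries no test. The plan calls Secondary Aim #1 exploratory and acknowledges its limited power.

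**The concern.** The screen works on the pooled effect of a component, while moderation is a difference between strata. If a component helps one stratum and does nothing in the other, its pooled effect shrinks to the stratum's share of the full effect. That can be too small to pay the BIC penalty. The component then leaves the model, and neither the interaction test nor the stratum fits bring it back.

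A component that works in early non-responders only, or in early responders only, would be a direct answer to the questions in section 3. It is also a case in which the committed analysis may report nothing by stratum. What is at stake is mainly the loss of stratum estimates and intervals for an exploratory objective, not a decisive test.

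**Working it through.** **Inputs.** From section 9.2: 280 eligible, 92% retained (280 × 0.92 = 257.6; 256 is used, 32 in each of 8 cells); SDs, pre-post correlations, MCIDs and detectable effects from the table. From section 3: 35%-45% responders; 40% is used, giving 102 responders and 154 non-responders.

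**Plan's own figure.** Detectable main effect = (2.241 + 0.842) × 2 × SD × √(1 − r²) / √257.6, at two-sided alpha 0.025 and 80% power. For Oswestry, 3.083 × 2 × 14.9 × √(1 − 0.49) / 16.05 = 4.09 (stated 4.12). For half the participants, × √2 = 5.78 (stated 5.83). For stiffness, 0.369 and 0.522 (stated 0.37 and 0.53). The table reproduces closely.

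**Standard errors.** Oswestry main effect: 4.12 / 3.083 = 1.336. Component-by-responder interaction: 1.336 / √(102/256 × 154/256) = 2.73.

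**Retention.** With the other two components null, BIC keeps a main effect roughly when |z| exceeds √ln 256 = 2.355.

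- Responders only, 6 points: pooled effect 6 × 102/256 = 2.39, z = 1.79, kept Φ(1.79 − 2.355) ≈ 29%.
- Non-responders only: pooled effect 6 × 154/256 = 3.61, z = 2.70, kept Φ(2.70 − 2.355) ≈ 63%.

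**Moderation power.** Ungated: Φ(6/2.73 − 1.96) ≈ 59% at alpha 0.05 (48% at 0.025; section 9.6 gives no alpha for this aim). The pooled estimate and the stratum difference are independent here, so gated power is retention × ungated power.

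| Oswestry effect (responders / non-responders) | Kept | Gated power | Ungated power |
|---|---|---|---|
| 6 / 0 | 29% | 17% | 59% |
| 0 / 6 | 63% | 38% | 59% |
| 6 / 3 | 78% | 15% | 20% |
| 0 / 0 (false signal) | 2% | 0.1% | 5% |

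A simulation over all 19 hierarchical models (200,000 trials per scenario) agrees to within about a point. A participant-level simulation with a baseline covariate gives 15% v 57%, 36% v 58% and 15% v 20% for the first three rows.

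**Responder share of 35%-45%.** Gated power is about 13%-23% (responders only) and 41%-33% (non-responders only), against 57%-61% ungated.

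**Other outcomes.** Same formulas, MCID or hypothesized effect in one stratum only, SE = stated main effect / 3.083:

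| Outcome | Responders only: kept; gated v ungated | Non-responders only: kept; gated v ungated |
|---|---|---|
| Global stiffness | 15%; 6% v 37% | 36%; 13% v 37% |
| Multifidus | 63%; 57% v 91% | 95%; 87% v 91% |
| Pain | 81%; 79% v 98% | 99%; 97% v 98% |

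**Sensitivity, Oswestry retention (responders only; non-responders only).**

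- Penalty counting 768 observations (256 × 3 visits): √ln 768 = 2.578, kept about 22%; 55%.
- A 5-point responder difference not absorbed by the 1-week adjustment: 26%; 60%.
- Both time points in the selection, effect persisting, assumed residual correlation 0.4-0.6: 12%-15%; 42%-50% with time-specific terms, or 35%-40%; 74%-80% with a common effect.
- Time-specific terms, effect halving by 3 months: 9%; 32%.

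**The case against.** **The scenario is extreme.** A full MCID in one stratum and nothing in the other is not predicted anywhere in the plan. With 6 and 3 points the gate costs about 5 percentage points or less in the single-time-point calculation. This stands, and it limits the point to effects largely confined to one stratum.

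**Screening is a defensible trade.** The plan wants a parsimonious model, and the gate has a real benefit. For a component with no effect in either stratum, it cuts the false moderation rate from 5% to about 0.1% per test. This also stands, and it is the price of the fix.

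**There is another route.** The optional modelling under Secondary Aim #2 could pick up responder-dependent effects. It is only something the team may do, so it is no substitute for a committed estimate.

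**The aim is exploratory.** Even ungated, Oswestry moderation power is only moderate and stiffness power is low. That lowers the priority, but an exploratory aim depends on reported estimates and intervals, and those are what the gate can remove.

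**A stronger reading.** A reader might infer that section 9.2 contradicts section 9.6, because it sizes "main effects of the 3 components in subgroup analyses involving half the participants" and claims at least 80% power "and for analyses of main effects in subgroups and conditional comparisons for each outcome except global stiffness". The documents do not support that. Section 9.2 never names responder status as the subgroup. Half the sample is not the 35%-45% expected for responders, and section 9.6 also mentions median splits, which do give halves. On the plan's SE, power for 6 Oswestry points at alpha 0.025 is Φ(6 / (1.336/√0.5) − 2.241) ≈ 82% in half the participants, but about 72% in a 40% stratum. Section 9.2 is supporting context only.

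**Conclusion.** The point holds in a limited form. As written, a component dropped by a selection that ignores responder status gets no committed moderation test and no responder or non-responder estimate for that outcome. Oswestry and global stiffness are the outcomes most exposed. Multifidus and pain are affected much less, except when the effect is confined to responders.

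The figures are approximations. They rest on the section 9.2 variances, a 40% responder share, a single 4-week analysis, the other components being null, and alpha 0.05 for the interaction. The plan does not state the sample size in the BIC penalty or how the selection treats the two follow-up times. Across the readings tried, Oswestry retention runs from 9% to 40% for responders only and from 32% to 80% for non-responders only. The direction does not change.

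A reader might also infer that the primary conclusions are at risk. They are not, because the primary-aim tests use the full factorial model with all three components. This is a worthwhile, low-cost change to an exploratory analysis, at the lower end of what should be changed.

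**What to change.** In section 9.6, Secondary Aim #1:

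- Prespecify the three component-by-responder interactions for every outcome, and report them with confidence intervals whatever BIC retains.
- Keep all three component main effects in the separate responder and non-responder fits.
- Keep the exploratory label. Keep the BIC-simplified model for Secondary Aim #2 and as an additional display.

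The cost is SAP wording and a little programming, with no added participants or data. The downside is multiplicity: up to 3 interactions × 4 outcomes × 2 time points = 24 exploratory tests, or 24 × 0.05 = 1.2 expected chance positives if there is no moderation (0.6 at alpha 0.025). The present gate nearly removes these for components with no effect in either stratum. Reporting all 24 estimates with intervals lets readers judge any isolated positive.
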